12.6 Amendments to the Protocol

Should amendments to the protocol be required, the amendments will be originated and documented by the Principal Investigator. It should also be noted that when an amendment to the protocol substantially alters the study design or the potential risk to the patient, a revised consent form might be required. The written amendment, and if required the amended consent form, must be sent to the IRB for approval prior to implementation.

12.7 Record Retention

Study documentation includes all Case Report Forms, data correction forms or queries, source documents, Sponsor-Investigator correspondence, monitoring logs/letters, and regulatory documents (e.g., protocol and amendments, IRB correspondence and approval, signed patient consent forms). Source documents include all recordings of observations or notations of clinical activities and all reports and records necessary for the evaluation and reconstruction of the clinical research study. Government agency regulations and directives require that all study documentation pertaining to the conduct of a clinical trial must be retained by the study investigator. In the case of a study with a drug seeking regulatory approval and marketing, these documents shall be retained for at least two years after the last approval of marketing application in an International Conference on Harmonization (ICH) region. In all other cases, study documents should be kept on file until three years after the completion and final study report of this investigational study.

Appendix A. GUIDANCE ON CONTRACEPTION

ACCEPTABLE METHODS FOR PROTOCOLS WITH A TERATOGENIC DRUG OR WHEN THERE IS INSUFFICIENT INFORMATION TO DETERMINE TERATOGENICITY

(CHOOSE ONE OF THE FOLLOWING 3 OPTIONS)^a

- OPTION 1: Any TWO of the following methods
 - Hormonal methods of contraception^{b, c, d}
 - IUD^{c, d, e}
 - Vasectomy^{d, f}
 - Tubal Ligation^d
 - A Barrier method (Female or Male Condom with spermicide, Cervical Cap with spermicide, Diaphragm with spermicide)
- OPTION 2: Male condom (with spermicide) and diaphragm^g
- OPTION 3: Male condom (with spermicide) and cervical cap^g

^a The theoretical failure rate for any of the options listed is considerably less than 1% per year

^b Excludes progestin-only pills

^c Hormonal contraceptives may not be used for contraception unless a drug-drug interaction study has demonstrated that the pharmacokinetics of the hormone based contraceptive has not been adversely affected by the investigational drug in the protocol or there is compelling evidence to substantiate that investigational product(s) or con-meds will not adversely affect contraception effectiveness. The use of hormone based contraceptives is not otherwise restricted.

^d A highly effective method of birth control with a failure rate less than 1% per year.

^e IUDS used should have a failure rate less than 1% (highly effective method), such as Mirena and ParaGard.

^f Must be at least 90 days from date of surgery with a semen analysis documenting azoospermia.

^g These 2 barrier methods together are acceptable for a teratogenic drug.

UNACCEPTABLE METHODS OF CONTRACEPTION

- No method
- Withdrawal
- Rhythm
- Vaginal Sponge
- Any barrier method without spermicide
- Spermicide
- Progestin only pills
- Concomitant use of female and male condom

Appendix B. Immune-related toxicity management algorithms.

These general guidelines constitute guidance to the Investigator and may be supplemented by discussions with the Medical Monitor representing the Sponsor. The guidance applies to all immuno-oncology agents and regimens.

A general principle is that differential diagnoses should be diligently evaluated according to standard medical practice. Non-inflammatory etiologies should be considered and appropriately treated.

[figure not shown]
Corticosteroids are a primary therapy for immuno-oncology drug-related adverse events. The oral equivalent of the recommended IV doses may be considered for ambulatory patients with low-grade toxicity. The lower bioavailability of oral corticosteroids should be taken into account when switching to the equivalent dose of oral corticosteroids.

Consultation with a medical or surgical specialist, especially prior to an invasive diagnostic or therapeutic procedure, is recommended.

The frequency and severity of the related adverse events covered by these algorithms will depend on the immuno-oncology agent or regimen being used.

GI Adverse Event Management Algorithm

Rule out non-inflammatory causes. If non-inflammatory cause is identified, treat accordingly and continue I-O therapy. Opiates/narcotics may mask symptoms of perforation. Infliximab should not be used in cases of perforation or sepsis.

Patients on IV steroids may be switched to an equivalent dose of oral corticosteroids (e.g. prednisone) at start of tapering or earlier, once sustained clinical improvement is observed. Lower bioavailability of oral corticosteroids should be taken into account when switching to the equivalent dose of oral corticosteroids.

Updated 05-Jul-2016

Renal Adverse Event Management Algorithm

[figure not shown]
Rule out non-inflammatory causes. If non-inflammatory cause, treat accordingly and continue I-O therapy

Patients on IV steroids may be switched to an equivalent dose of oral corticosteroids (e.g. prednisone) at start of tapering or earlier, once sustained clinical improvement is observed. Lower bioavailability of oral corticosteroids should be taken into account when switching to the equivalent dose of oral corticosteroids.

Pulmonary Adverse Event Management Algorithm

Rule out non-inflammatory causes. If non-inflammatory cause, treat accordingly and continue I-O therapy. Evaluate with imaging and pulmonary consultation.

[figure not shown]

Patients on IV steroids may be switched to an equivalent dose of oral corticosteroids (e.g. prednisone) at start of tapering or earlier, once sustained clinical improvement is observed. Lower bioavailability of oral corticosteroids should be taken into account when switching to the equivalent dose of oral corticosteroids.

Updated 05-Jul-2016

Hepatic Adverse Event Management Algorithm

Rule out non-inflammatory causes. If non-inflammatory cause, treat accordingly and continue I-O therapy. Consider imaging for obstruction.

[figure not shown]
Patients on IV steroids may be switched to an equivalent dose of oral corticosteroids (e.g. prednisone) at start of tapering or earlier, once sustained clinical improvement is observed. Lower bioavailability of oral corticosteroids should be taken into account when switching to the equivalent dose of oral corticosteroids.

*I-O therapy may be delayed rather than discontinued if AST/ALT ≤ 8 x ULN or T.bili ≤ 5 x ULN.

**The recommended starting dose for grade 4 hepatitis is 2 mg/kg/day methylprednisolone IV.

Skin Adverse Event Management Algorithm

Rule out non-inflammatory causes. If non-inflammatory cause, treat accordingly and continue I-O therapy.

[figure not shown]
Patients on IV steroids may be switched to an equivalent dose of oral corticosteroids (e.g. prednisone) at start of tapering or earlier, once sustained clinical improvement is observed. Lower bioavailability of oral corticosteroids should be taken into account when switching to the equivalent dose of oral corticosteroids.

*Refer to NCI CTCAE v4 for term-specific grading criteria.

^If SJS/TEN is suspected, withhold I-O therapy and refer patient for specialized care for assessment and treatment. If SJS or TEN is diagnosed, permanently discontinue I-O therapy.

Neurological Adverse Event Management Algorithm

[figure not shown]
Rule out non-inflammatory causes. If non-inflammatory cause, treat accordingly and continue I-O therapy.

Patients on IV steroids may be switched to an equivalent dose of oral corticosteroids (e.g. prednisone) at start of tapering or earlier, once sustained clinical improvement is observed. Lower bioavailability of oral corticosteroids should be taken into account when switching to the equivalent dose of oral corticosteroids.

Endocrinopathy Management Algorithm

Rule out non-inflammatory causes. If non-inflammatory cause, treat accordingly and continue I-O therapy. Consider visual field testing, endocrinology consultation, and imaging.

Patients on IV steroids may be switched to an equivalent dose of oral corticosteroids (e.g. prednisone) at start of tapering or earlier, once sustained clinical improvement is observed. Lower bioavailability of oral corticosteroids should be taken into account when switching to the equivalent dose of oral corticosteroids.

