5.3.5 Management of Immune-Related Toxicities

Treatment of immune-related adverse events (irAEs) should follow guidelines set forth in the following tables. Also, please refer to Appendix B for details.

Table 6. Dose Modification and Management of irAEs

Gastrointestinal irAEs (e.g. diarrhea, colitis)		
Observation	Management	Follow-up
Grade 1 AE	Continue nivolumab therapy. Consider symptomatic treatment (e.g. loperamide, hydration, electrolyte replacement).	Close monitoring for worsening symptoms. Educate patient to report worsening immediately. If worsens: Treat as Grade 2 or 3/4
Grade 2 AE	Delay nivolumab therapy. Symptomatic treatment.	If improves to Grade 1: Resume nivolumab therapy. If no improvement within 5-7 days or recur: Consider starting IV methylprednisolone 0.5-1.0 mg/kg/day or oral equivalent. Once improving, taper steroids over ≥ 1 month and consider prophylactic antimicrobials for opportunistic infections, and consider resuming nivolumab. If the event is not responsive within 3-5 days or worsens despite steroid: Treat as Grade 3/4.
Grade 3 to 4 AE	Discontinue nivolumab therapy. 1.0 to 2.0 mg/kg/day methylprednisolone IV or equivalent. Consider urgent GI consult and imaging and/or colonoscopy as appropriate.	Once improving, taper steroids over ≥ 1 month and consider prophylactic antimicrobials for opportunistic infections. If still no improvement within 3-5 days or recurs after improvement despite steroid: consider adding further immunosuppressives (e.g. infliximab at 5mg/kg once every 2 weeks if no contraindication). Caution: Consider GI

		consult to rule out bowel perforation and refer to infliximab label for general guidance before using infliximab. Infliximab should not be used in cases of perforation or sepsis.
--	--	--

Dermatological irAEs		
Observation	Management	Follow-up
Grade 1-2 AE	Symptomatic therapy (e.g. oral antihistamines, topical steroids). Continue nivolumab therapy.	If persists > 1-2 weeks or recurs: Consider delaying nivolumab. Consider skin biopsy. Consider 0.5-1.0 mg/kg/day methylprednisolone IV or oral equivalent. Once improving, taper steroids over \geq 1 month, consider prophylactic antimicrobials for opportunistic infections, and resume nivolumab. If worsens: Treat as Grade 3-4.

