Grade 3 to 4 AE	
Discontinue nivolumab therapy*
 
Regular and frequent checking of LFTs (e.g. every 1-2 days) until elevations of these are improving or resolved.
 
1.0 to 2.0 mg/kg/day methylprednisolone IV or IV equivalent**
 
Add prophylactic antimicrobials for opportunistic infections.
 
Consult gastroenterologist.
	
If returns to Grade 2 or better: Taper steroids over \geq 1 month.
 
If does not improve in > 3 to 5 days, worsens or rebounds: Add mycophenolate mofetil 1 gram (g) twice daily. If no response within an additional 3 to 5 days, consider other immunosuppressants per local guidelines.

*Nivolumab therapy may be delayed rather than discontinued if AST/ALT \leq 8 x ULN and Total bilirubin \leq 5 x ULN.

**The recommended starting dose for grade 4 hepatitis is 2 mg/kg/day methylprednisolone IV.

Endocrine irAEs		
Endocrine Disorder	Management	Follow-up
Asymptomatic TSH elevation	
Continue nivolumab therapy.
 
If TSH < 0.5 x LLN, or TSH > 2 x ULN, or consistently out of range in 2 subsequent measurements: include free T4 at subsequent cycles as clinically indicated; consider endocrinology consult.
	
Symptomatic endocrinopathy	
Evaluate endocrine function.
 
Consider pituitary scan.
	
If improves (with or without hormone replacement): Taper steroids over \geq 1 month and consider prophylactic antimicrobials for opportunistic infections.
 
Resume nivolumab therapy.

	
Symptomatic with abnormal lab / pituitary scan: Delay nivolumab therapy. 1 to 2 mg/kg/day methylprednisolone IV or by mouth equivalent. Initiate appropriate hormone therapy.
 
No abnormal lab / pituitary MRI scan but symptoms persist: Repeat labs in 1 to 3 weeks / MRI in 1 month
	
Subjects with adrenal insufficiency may need to continue steroids with mineralocorticoid component.

Suspicion of adrenal crisis (e.g. severe dehydration, hypotension, shock out of proportion to current illness)
	
Delay or discontinue nivolumab therapy.
 
Rule out sepsis.
 
Stress dose of IV steroids with mineralocorticoid activity.
 
IV fluids.
 
Consult endocrinologist.
 
If adrenal crisis ruled out, then treat as above for symptomatic endocrinopathy.
	

Renal irAEs		
Observation	Management	Follow-up

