5.5 Off-treatment criteria

Treatment may continue until one of the following criteria applies:

- Disease progression and investigator determination that the subject is no longer benefiting from study treatment*
- Any AE that meets criteria for discontinuation as defined in section 5.3.
- Patient decides to withdraw from the study.
- General or specific changes in the patient's condition render the patient unfit for further treatment in the judgment of the investigator.
- Patient is non-compliant with the protocol guidelines.

* Patients are allowed to stay on treatment beyond progression if the investigator thinks that the patient is still benefiting from the treatment.

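### Table 6 and Appendix B give different rules for delaying rather than stopping nivolumab in a severe hepatic immune-related event: one joins the two liver limits with *and*, the other with *or*

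*Combined protocol and SAP*

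**What the plan says.** Section 5.3.5, Table 6 (hepatic irAEs) sets the default action for a grade 3 to 4 event: "Discontinue nivolumab therapy". An asterisk on that cell leads to an exception, which begins "Nivolumab therapy may be delayed rather than discontinued if AST/ALT". It sets limits of 8 x ULN for AST/ALT and 5 x ULN for total bilirubin, and the connecting words are "8 x ULN and Total bilirubin". Both limits have to be met.

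Appendix B, in the footnotes to its hepatic algorithm, states the exception again: "I-O therapy may be delayed rather than discontinued if AST/ALT ≤ 8 x ULN or T.bili ≤ 5 x ULN". Either limit is enough.

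Three other places bear on which text a site should follow:

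- Section 5.3.5 opens by telling sites to manage irAEs by its tables, and then adds: "Also, please refer to Appendix B for details".
- Section 5.5 lists among the reasons for ending treatment: "Any AE that meets criteria for discontinuation as defined in section 5.3".
- Appendix B introduces itself with: "These general guidelines constitute guidance to the Investigator".

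**The concern.** The footnote decides whether nivolumab is stopped or only withheld for a time in a patient with a severe liver event. The two versions use the same analytes, limits and inequality signs and differ only in the connector, which is the word that settles the outcome. An investigator who opens Appendix B, as Section 5.3.5 directs, finds an explicit permission to delay that Table 6 does not give.

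The *or* version also weakens the rule sharply. It lets a low bilirubin excuse any transaminase level, so a patient with very high AST/ALT could be kept eligible for more nivolumab where Table 6 calls for discontinuation.

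Section 12.5 requires the study to be run exactly as the approved protocol describes. With two versions in the protocol, it is also unclear whether a delay based on Appendix B is a deviation.

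**Working it through.** There is no stated figure to reproduce. The check is a comparison of two logical rules.

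**Inputs.** Let A be AST/ALT and B be total bilirubin, both in multiples of ULN.

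- Table 6 footnote: delay is allowed if A ≤ 8 **and** B ≤ 5; otherwise discontinue.
- Appendix B hepatic footnote: delay is allowed if A ≤ 8 **or** B ≤ 5; otherwise discontinue.

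**Are these the same rule?** The Appendix B flow chart is not shown, so the box carrying its asterisk cannot be seen. But an exception that replaces stopping with delay only makes sense where stopping is the default. In the hepatic part of Table 6 that is the grade 3 to 4 row alone. The next footnote, on the steroid starting dose for grade 4 hepatitis, gives the same dose (2 mg/kg/day) in both places. The two sets of footnotes are parallel.

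**All four combinations, with an example of each:**

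| AST/ALT | Bilirubin | Example (A, B) | Table 6 | Appendix B | Agree? |
|---|---|---|---|---|---|
| ≤ 8 | ≤ 5 | (7, 4) | may delay | may delay | yes |
| > 8 | ≤ 5 | (9, 4) | discontinue | may delay | **no** |
| ≤ 8 | > 5 | (7, 6) | discontinue | may delay | **no** |
| > 8 | > 5 | (9, 6) | discontinue | discontinue | yes |

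The texts differ in 2 of 4 cells, those where exactly one limit is exceeded. In both, Appendix B is the less strict. It can never be the stricter text, because any patient who meets both limits also meets at least one.

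**Isolated transaminase rise.** Hold B at 1 and let A increase:

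| (A, B) | Table 6 | Appendix B |
|---|---|---|
| (9, 1) | discontinue | may delay |
| (15, 1) | discontinue | may delay |
| (25, 1) | discontinue | may delay |

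Under *or*, the condition B ≤ 5 is already satisfied, so the 8 x ULN limit never acts, however high AST/ALT goes.

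**A case against the protocol's own liver-injury thresholds.** Take A = 25 and B = 4. Both values exceed the levels that Section 8.1.4 uses for potential drug-induced liver injury (AST/ALT > 3 x ULN and bilirubin > 2 x ULN), which is a serious adverse event if the remaining conditions are met. Appendix B, read literally, would still allow a delay, since 4 ≤ 5. Table 6 would not, since 25 > 8.

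**The case against.** **Table 6 already governs in substance.** Section 5.3.5 tells sites to follow its tables, Section 5.3.1 points to 5.3.5 for holding nivolumab, Section 5.5 ties the end of treatment to Section 5.3, and Appendix B calls itself guidance and covers all immuno-oncology agents. This stands in large part: Table 6 does have the stronger claim. But no sentence says that it prevails, Section 5.3.5 calls its own tables guidelines, and it sends the reader to Appendix B for detail.

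**Delay and discontinuation both withhold the drug during the event.** The other Table 6 measures (frequent liver tests, steroids, a gastroenterology consult) apply either way, and harm would need a later restart, for which neither footnote gives a rule. This too is fair, and it limits what can be claimed. Still, a delay leaves a restart open and a discontinuation does not.

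***Or* could be read analyte by analyte:** up to 8 x ULN if the transaminases are the problem, up to 5 x ULN if bilirubin is. On that reading the conflict shrinks or disappears. The documents do not state that reading, and a stopping rule should not depend on it.

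**The flow chart is not shown.** This is true, and it leaves the grade marked by the Appendix B asterisk unseen. The footnote itself is complete and legible, and its wording is what conflicts with Table 6.

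**Conclusion.** The inconsistency is real and sits in current, legible text. For a hepatic event that would otherwise require stopping nivolumab, the protocol gives two answers whenever exactly one of the two limits is exceeded, and Appendix B is the more permissive each time.

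This rests on reading *and* and *or* literally, and on the Appendix B exception applying, as in Table 6, where discontinuation is the default.

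The practical reach is limited. A site that discontinues complies with both texts; the exposure is a site that relies on Appendix B to delay. The documents give no rate for such events, so the number of patients cannot be estimated; it is probably small. No effect on DLT calls or on the PFS analysis is claimed. It should be corrected as a safety instruction, but it does not threaten the validity of the trial.

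**What to change.** In the Appendix B hepatic footnote, replace *or* with *and*, so that a delay needs AST/ALT ≤ 8 x ULN and bilirubin ≤ 5 x ULN. This matches Table 6 and is the safer rule.

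Add one sentence to Section 5.3.5: *Where Table 6 and Appendix B differ, Table 6 governs.* If Appendix B has to stay unaltered as a standard text, that sentence alone resolves the conflict.

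The cost is one word, one sentence and a short notice to sites. No procedures, visits or patients are added.

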Appendix C. ECOG Performance Status Score

ECOG Performance Status Scale		Karnofsky Performance Scale	
Grade	Descriptions	Percent	Description
0	Normal activity. Fully active, able to carry on all pre-disease performance without restriction.	100	Normal, no complaints, no evidence of disease.
		90	Able to carry on normal activity; minor signs or symptoms of disease.
1	Symptoms, but ambulatory. Restricted in physically strenuous activity, but ambulatory and able to carry out work of a light or sedentary nature (e.g., light housework, office work).	80	Normal activity with effort; some signs or symptoms of disease.
		70	Cares for self, unable to carry on normal activity or to do active work.
2	In bed <50% of the time. Ambulatory and capable of all self-care, but unable to carry out any work activities. Up and about more than 50% of waking hours.	60	Requires occasional assistance, but is able to care for most of his/her needs.
		50	Requires considerable assistance and frequent medical care.
3	In bed >50% of the time. Capable of only limited self-care, confined to bed or chair more than 50% of waking hours.	40	Disabled, requires special care and assistance.
		30	Severely disabled, hospitalization indicated. Death not imminent.
4	100% bedridden. Completely disabled. Cannot carry on any self-care. Totally confined to bed or chair.	20	Very sick, hospitalization indicated. Death not imminent.
		10	Moribund, fatal processes progressing rapidly.
5	Dead.	0	Dead.

ASSESSMENT/EVENT	Screening	Treatment Period*									
		C1	C1	C1	C1	C2 and beyond	C2 and beyond	C2 and beyond	C2 and beyond	EOT	Follow-up
Study Visit		D1	D15	D29	D43	D1	D15	D29	D43		
Informed consent	X										
ECOG PS	X	X	X	X	X	X	X	X	X	X	
History and physical examination	X	X	X	X	X	X	X	X	X	X	
Adverse event assessments		X	X	X	X	X	X	X	X	X	
Vital Signs	X	X	X	X	X	X	X	X	X	X	
Height and weight	X										
Concomitant Medications Collection	X	X	X	X	X	X	X	X	X	X	
12 Lead ECG	X										
Tumor imaging ^a	X					X					
Brain imaging (MRI or CT)	X	To be performed as clinically indicated at the discretion of the investigator									
FDG-PET	X	To be performed as clinically indicated at the discretion of the investigator									
NETSPOT PET ^b	X					X ^c					
CBC with differential	X	X ^j	X	X	X	X	X	X	X	X	
PT/aPTT	X										
Comprehensive Metabolic Panel	X	X ^j	X	X	X	X	X	X	X	X	
Thyroid function test ^d	X			X		X		X		X	
LDH	X	X ^j	X	X	X	X	X	X	X	X	
Magnesium	X	X ^j	X	X	X	X	X	X	X	X	
Phosphorus	X	X ^j	X	X	X	X	X	X	X	X	
Amylase	X										
Lipase	X										
HBsAg ^e	X										
anti-HCV ^e	X										
anti-HIV ^e	X										
Pregnancy test ^f	X		X ^f				X ^f				
Tumor biopsy	X ^g	Optional at the time of progression									
Nivolumab ^h		X	X	X	X	X	X	X	X		
¹⁷⁷ Lu-DOTA ⁰ -Tyr ³ -Octreotate			X				X ^h				
Long-term follow up including survival											X ⁱ

- a: Initial tumor assessment will be performed at C2 D1 (\pm 7 days) and every 8 weeks (\pm 7 days) thereafter.
 - b: Refer to section 6.1 for details
 - c: On treatment Netspot only on cycle 2 day 1 (\pm 3 days)
 - d: Thyroid function testing will be done every cycle on day 1 (\pm 3 days) and day 29 (\pm 3 days). Does not need to repeat on C1D1.
 - e: Within three months prior to starting study treatment
 - f: Only for women of child bearing potential (WOCBP). Within 24 hours prior to the administration of $^{177}\text{Lu-DOTA}^0\text{-Tyr}^3\text{-Octreotate}$.
 - g: Optional. Utilization of archival tissue will be allowed.
 - h: May be given one day earlier or delayed up to 1 week. $^{177}\text{Lu-DOTA}^0\text{-Tyr}^3\text{-Octreotate}$ will only be given for 4 cycles.
 - i: Annually for two years
 - j: C1D1 laboratory tests do not need to be repeated if the screening laboratory tests were done within 7 days from C1D1.
- * Refer to section 6.2 for details about time windows within which each procedure should be performed.

